5.2 Inclusion criteria

Participants will meet ALL the following:

- The individual meets the diagnostic or treatment criteria set out in TABLE 2 on page 13.
- 18 years or older.
- The individual must have capacity to provide written informed consent or in cases where this is not possible, a legal representative or Welfare Attorney who is able to make an informed decision on their behalf.

5.3 Exclusion criteria

Participants will meet NONE of the following:

- Does not have a legal representative who is able to make an informed decision about consent to the study.
- Individuals will be excluded if they have received any monoclonal antibody therapy against SARS-CoV-2 within the 26 weeks prior to the first study blood sampling (either as a treatment for infection or pre-exposure prophylaxis). Recipients of regular immunoglobulin therapy are eligible*.
- Age less than 18 years.

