6.2 Participant identification

Potentially eligible participants (based on underlying conditions) will be identified either through hospital clinics, local hospital clinical databases, localised adverts or through the existing local or ethically approved studies, where patient has given prior consent to be contacted to participate in future studies. They will be contacted either by post, telephone, email, or in-person during routine clinic visits and invited to join the study. They will receive a PIS and copy of the consent form either by post, email or in-person from a member of the study team or clinical team.

Participants whom are not known to local study sites also be able to self-identify for the STRAVINSKY study via the STRAVINSKY webpage and posters and other social media outlets featuring QR codes. Participants will contact the study team through the study email [contact]. The Central Study Team will confirm eligibility. Where possible, we will include individuals that attend the chosen clinical sites to enable access to hospital records, however, for those that self-identify and self-consent in the community (having read and agreed to the participant information sheet) we will request clarification of their clinical history through GP data sources and via access to the National Immunisation and Vaccination System and NHS digital clinical data through their NHS/CHI number.

Informed consent and data collection will be collected online via a REDCap database. Patients and sites without access to devices or internet will be consented via telephone or face to face and the data will be transcribed into the REDCap database. Any case report form (CRF) data collected face to face or via telephone will also be transcribed into the database by each local clinical care team. Copies of all paper CRF data and consent forms must be kept in the site master file for the duration of the study.

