6.3.1 Arrangements for individuals who do not have capacity to consent

Some patients may not have the capacity to consent, e.g. individuals in the learning disability group. For these individuals, the clinician will inform the patient's next of kin, personal consultee or legal representative /Welfare Attorney about the study either through telephone call or face to face at the time of recruitment. If the next of kin or personal consultee is not be able to come to the hospital, the research team will send the consultee information sheet and consultee declaration form to them either by post or email. The research team will then obtain the declaration form from the personal consultee or welfare attorney by telephone call witnessed by another member of the research team.

The potential participants will be provided with a simplified poster outlining the study. If they would like to participate, participants' representatives will be given sufficient time to review the PIS and will be given the opportunity to ask questions, once they are able to make an informed decision they will be asked to sign a consent form.

This alternative arrangement will enable vulnerable adults to participate in this study and so inform care for individuals within these disease groups.

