22.0 Appendix 2 Visit Summary

Timing	VISIT	Checklist	Responsibility (Local Study Team (L) or Central Study Team (C) or Participant (P)	
			Remote Cohort	In-person cohort
	PARTICIPANT IDENTIFICATION	Offer PIS	L	L
	SCREENING*	1) Informed Consent	P with L assistance if needed.	P with L assistance if needed.
		2) Check and confirm eligibility	P	P
		3) Trial registration onto REDCap	C/L	C/L
		4) Supply participants with Central Study Team contact details	C/L	C/L
As soon as possible after consent	VISIT 1	1) Complete online CRF	L	L
		2) Blood sampling	Р	L
		3) Nasal swab COVID-19 test kit	Provided by C, returned by P	by C, returned
		4) Antibody or swab result reported to patient		by P C
Remote cohort: Ideally 1 week before booster vaccine	VISIT 2	1) Complete online CRF	P with L assistance if needed.	L
In-person cohort: As above, but this visit can be omitted if it is less than 12 weeks after VISIT 1		2) Blood sampling	P	L
4-10 weeks post booster vaccine	VISIT 3	1) Complete online CRF	P with L assistance if needed.	L
		2) Blood sampling	Р	L
24-36 weeks post booster vaccine	VISIT 4	1) Complete online CRF	P with L assistance if needed.	L
		2) Blood sampling	Р	L
Anytime during study	ANYTIME	1. Participant to inform Central Study	P	P

	2.	Team if they have a COVID- 19 infection Return of		
	۷.	nasal swab to be repeated 2 weekly till negative	Provided by C, returned by P	Provided by C, returned by P

^{*}Individuals who self identifies for participation AND who are not registered with one of the participating sites will have their screening activities managed by the Central Study Team

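### The first exclusion in 5.3 is not conditional on lacking capacity, and 5.2 and 5.3 leave out the personal consultee on whose declaration 6.3.1 enrols

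*Protocol*

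**What the plan says.** Section 5.3 opens its list with "Participants will meet NONE of the following", so meeting any one item excludes a person. The first item is "Does not have a legal representative who is able to make an informed decision about consent to the study". The exclusion list in the Study Summary (section 1.0) carries the same item.

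Section 5.2 sets the matching inclusion rule: "The individual must have capacity to provide written informed consent or in cases where this is not possible, a legal representative or Welfare Attorney", the latter being someone able to decide on the person's behalf. The Study Summary version of this criterion names only a legal representative.

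Sections 6.2 and 6.3 describe participants consenting for themselves. Section 6.2 has a route "for those that self-identify and self-consent in the community", and 6.3 has individuals sign an online or paper form.

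Section 6.3.1 covers adults who cannot consent, with the learning disability group as its example. The clinician informs the "next of kin, personal consultee or legal representative /Welfare Attorney about the study". If the next of kin or personal consultee cannot come to the hospital, "the research team will send the consultee information sheet and consultee declaration form to them either by post or email". The last step is: "The research team will then obtain the declaration form from the personal consultee or welfare attorney by telephone call".

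In Appendix 2 (Visit Summary), the screening row "2) Check and confirm eligibility" is assigned to the participant in both cohorts. A footnote gives the screening of self-referrers who are not registered at a participating site to the Central Study Team.

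**The concern.** Eligibility criteria should give the same answer wherever they are applied. Here they do not, in two ways.

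First, the exclusion lacks the condition that the person lacks capacity. Most of the cohort is expected to consent personally, and a competent adult need not have a legal representative. Such a person satisfies 5.2 and fails 5.3.

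Second, the sections disagree on who may act for an adult without capacity. Section 6.3.1 relies on a personal consultee, a role that neither 5.2 nor 5.3 names. A site working from the criteria could decline a person whom a site working from 6.3.1 would enrol. Someone enrolled on a consultee declaration alone could later be challenged as ineligible. That challenge would go to the basis on which an adult without capacity was entered, so the point is more than tidiness. The group most exposed is group 6, a planned stratum of 120-140. Group 7 may also be touched, since its footnote admits severe complex neurodisability.

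**Working it through.** No formula applies: the point depends on no alpha, power, rate or effect size, and the plan states no figure to reproduce. The check is to apply the wording literally to each kind of person.

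**Who may act for an adult without capacity**

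| Place in the protocol | Persons named |
|---|---|
| Study Summary, inclusion | legal representative |
| Section 5.2, inclusion | legal representative or Welfare Attorney |
| Study Summary and 5.3, exclusion | legal representative |
| Section 6.3.1, who is informed | next of kin, personal consultee, or legal representative/Welfare Attorney |
| Section 6.3.1, who gives the declaration | personal consultee or welfare attorney |

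**Result for each case**

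| Case | 5.2 | 5.3 | Consent route |
|---|---|---|---|
| 1. Has capacity, no legal representative | met | excluded | self-consent, 6.2 and 6.3 |
| 2. Has capacity and a legal representative | met | not excluded | self-consent |
| 3. Lacks capacity, has a legal representative | met | not excluded | provided for in 6.3.1 |
| 4. Lacks capacity, has only a personal consultee | not met | excluded | provided for in 6.3.1 |
| 5. Lacks capacity, has nobody | not met | excluded | none |

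Cases 2, 3 and 5 are consistent. Cases 1 and 4 are not.

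- **Case 1.** The inclusion criterion is an either/or, with capacity as the first branch. The exclusion negates only the second branch and drops the condition that brings it into play.
- **Case 4.** Section 6.3.1 joins the personal consultee to the legal representative by an 'or', so the text treats them as different roles. No definition of legal representative elsewhere takes in a consultee. Correcting 5.3 alone would leave 5.2 in conflict with 6.3.1.

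**Next of kin.** Section 6.3.1 informs the next of kin and may send them the consultee papers, but its declaration step does not name them. Whether a next of kin can act other than as personal consultee is left open.

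**Number affected.** The protocol gives the planned size of group 6 (120-140). It does not give the share who lack capacity, or the share of those who have only a consultee. The count in case 4 therefore cannot be computed.

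**The case against.** The strongest reply is that no site would misapply the first half. Section 5.2 brings in a representative only where the person's own consent is not possible, and 6.2 and 6.3 describe self-consent throughout. The exclusion is plainly meant as the negative of that fallback. This stands. A reader might infer that the exclusion bars adults with capacity in general, or that recruitment across all 20 groups is at risk. The documents do not support that: even literally, it reaches only those without a legal representative, and the intended meaning is easily recovered.

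On the second half, legal representative is undefined. Section 5.3 describes the role by function, and 6.3.1 also speaks loosely of participants' representatives, so a broad reading that takes in a consultee is possible. Section 6.3.1 is also the specific text on incapacity, and a site could simply follow it. This carries some weight, but the alternatives listed in 6.3.1 point the other way, and eligibility should not turn on an undefined term.

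Three further inferences go too far:

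- **That 6.3.1 enrols on the word of a next of kin alone.** Its declaration step names only the personal consultee or welfare attorney.
- **That Appendix 2 leaves lay people to decide eligibility, against 6.2.** Its footnote already gives unregistered self-referrers to the Central Study Team, as 6.2 does. For site patients, 6.2 has candidates identified through clinics and databases, and 6.5.1 lets the study team confirm clinical details from records. What remains is a table cell that does not match those checks.
- **That a known number of participants would be lost, or that group 6 will differ by site.** The first would need rates that the documents do not give. The second is a possible consequence and has not been shown.

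**Conclusion.** The point holds on the wording. In an operative criterion, the Study Summary and 5.3 omit the condition on capacity. This is a drafting error with a clear intent. The more substantive fault is that an adult without capacity who is supported only by a personal consultee can be enrolled under 6.3.1 and is ineligible under 5.2 and 5.3.

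This second conclusion rests on reading personal consultee and legal representative as distinct roles, as the list in 6.3.1 does. If the sponsor meant legal representative to include a consultee, the remedy is still to say so.

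The effect falls mainly in group 6 (planned 120-140). The number of people cannot be stated, and no sample size, power or alpha figure changes. The fault should be corrected because the criteria, followed as written, give wrong enrolment decisions and the correction costs almost nothing.

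**What to change.** 1. In the Study Summary and 5.3, replace the first exclusion with: *Lacks capacity to consent AND has no personal consultee, legal representative or Welfare Attorney able to act under section 6.3.1.*
2. In the Study Summary and 5.2, use the same list of persons in the inclusion criterion.
3. In 6.3.1, state whether a next of kin acts only when serving as personal consultee, and use the same list at the declaration step.
4. As a minor separate alignment, reconcile the Appendix 2 screening cell for site-registered patients with the study-team checks in 6.2 and 6.5.1. The footnote on unregistered self-referrers can stay.

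The cost is a few sentence-level edits in the next amendment. No added staff or data collection is needed, because confirmation of clinical details from records is already provided for at Visit 1.

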5.0 Study population and eligibility criteria

5.1 Patient selection

Participants in this study will have an underlying disorder which has identified them as being clinically vulnerable. The disease and treatment groups eligible for participation (**TABLE 2, page 13**) in STRAVINSKY may alter throughout the study depending on the results from the retrospective analysis or other new knowledge/discussions such as the report from the Independent Advisory Group for COVID-19 medicines.⁵

TABLE 2. Groups eligible for participation

Group	Disease related groups (n=120-140 per group)				
1	Chronic lymphoproliferative disorders (footnote 1)				
2	Plasma cell disorders (footnote 2)				
3	Myelodysplastic syndrome (MDS) or (myeloproliferative neoplasms MPN) (footnote 3)				
4	Sickle cell disease, thalassaemia, or rare inherited anaemias				
5	Active malignancy diagnosed within 2 years of study consent (excluding non-melanoma skin cancer, non-invasive bladder cancer and localized squamous cell carcinoma of cervix)				
	(Note: participants who have received radiotherapy or systemic anti-cancer treatment within the last 26 weeks should be included in groups 18 and 19 first).				
6	Down's syndrome and learning disability				
7	Neurological diseases (Parkinson's and mult	iple sclerosis) (footnote 4)			
8	HIV				
9	Common variable immunodeficiency an prophylactic antibiotics and/or immunoglob	d secondary immunodeficiency (requiring ulin)			
10	Cirrhosis (footnote 5)				
11	Chronic respiratory conditions (footnote 6)				
12	Chronic kidney disease (CKD) stage 4-5 (foot	note 7)			
13	Diabetes mellitus (Type 1 and 2)				
14	Cardiac failure				
	Treatment-related group	Timing			
	(n=120-140 per group)				
15	Previous recipients of a solid organ transplant (SOT)	At any time			
16	Recipient of a haematopoietic stem cell transplant (HSCT)	Within 52 weeks at time of study consent			
17	Recipient of B-cell depleting treatment (APPENDIX 1 for details)	Within 52 weeks at time of study consent			
18	Recipient of systemic anti-cancer therapy e.g. chemotherapy or immunotherapy and others (APPENDIX 1 for details)	Ongoing or within last 26 weeks at time of study consent			
19	Recipient of radiotherapy	Ongoing or within last 26 weeks at time of study consent			
20	Autoimmune disease on systemic immunosuppressive* medication (APPENDIX 1 for details)	Ongoing or within last 26 weeks at time of study consent			

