6.0 Prospective study

6.1 Study design and overview

This is a multicentre prospective, observational cohort study (**FIGURE 1**). Patients will provide samples and clinical data on 4 different occasions over 12-18 months. For each of the 4 visits individuals will be allocated to be involved in the study either remotely or attend in-person.

3000 individuals will be recruited in total; for 2600 of these patients (remote cohort), their commitment to the study will be entirely remote.

400 individuals (in-person cohort) will be invited to attend a sampling appointment at one of the 4 inperson sampling sites (Birmingham, Southampton, Imperial or Oxford), for each of the 4 study visits. The aim will be to recruit between 120 and 140 individuals per disease/treatment group as detailed in **TABLE 2.**

13 | Page STRAVINSKY Protocol

^{*} This enables assessment of the primary outcome and response to bivalent vaccine. It is highly likely that policy on these licensed treatments will change, in which case we may submit an amendment to individuals receiving SARS-CoV-2 monoclonal Abs.

Informed consent and data collection will predominantly be collected online via a REDCap database. Patients and sites without access to devices or internet will be consented via telephone, the signed paper consent form will then be sent to the participant to counter sign, and they will be asked to post this back to the central study team.

Participants without access to devices to internet will also be offered face to face appointments where the patient can either be supported by the research nurse to complete the online consent form or the participant can sign a paper consent form. If paper consent forms are used, they will be transcribed/scanned into REDCap and the original paper source document will be stored at the recruiting site for the duration of the study. Any case report form (CRF) data collected face to face or via telephone will also be transcribed directly into the database by each local clinical care team. Paper CRF data and consent forms will be transcribed/scanned into REDCap. The original paper documents will be stored at the recruiting site.

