9.1 Anti-spike antibody testing

Antibodies will be tested using the Roche spike IgG quantitative assay (Birmingham). The assay detects anti-spike antibodies against the original Wuhan strain and so is suitable for detecting vaccine responses in a quantitative way. It will also detect antibodies following infection and cannot distinguish between these. It will be the primary platform to be used for all participants as it is already in widespread use by PHE and in the NHS. The Roche assay has been validated in Birmingham for DBS and shows excellent correlation and concordance with serum in providing a quantitative result. This remote sampling has been widely used for COVAD and other COVID-19 studies (PANORAMIC, COVIDENCE). To ensure applicability, the Roche assay performance will be compared with other platforms in use in the NHS using World Health Organisation (WHO) reference serum. This assay can be used to assess blood and mucosal samples.

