- · Occupation, nature of work and type of personal protective equipment used during that work
- Medical conditions (self- reported)
- latrogenic immunosuppression (or within 6 months of iatrogenic immunosuppression including chemotherapy)
- · Vaccination history including COVID-19, influenza, and any test vaccines given
- · Known prior infection

Behavioural variables

If the participant self-isolated as a result of an illness in a household contact, we will collect data on the nature of that illness (when was illness, symptoms, severity, duration) and how many other household contacts were unwell.

Serological response

Time points for serological measurements: Assessment at 4 timepoints (Visit 1: baseline visit, Visit 2: before next vaccine dose, visit 3: 4 weeks post vaccine dose and Visit 4: 24-36 weeks post vaccine).

ii) 'Low' antibody range: Antibody values which lie within the lower 10th percentile of range of IgG antibody concentrations in HC following vaccine dose.

General analysis principles

- Summary statistics will include either mean, standard deviation, and/or median, interquartile range for continuous variables as appropriate to the distribution and n (%) for frequencies.
- The amount of missing data will be reported. Analysis will be of complete data and missing data will not be imputed.
- 5% two-sided level of statistical significance, with corresponding 95% confidence intervals presented where applicable.
- No adjustments for multiplicity are planned.

Planned analyses and reporting:

Primary Outcome

To assess the additive value of serological responses to CV status in predicting infection

The binary infection outcome will be captured by recording the timing and incidence rates of all infections from ≥14 days post vaccination given between Visit 2 until Visit 4 will be reported in the total combined CV groups, and by individual CV groups. We will describe the number and proportion of infections for each level of antibody response post-V3 (no, low, normal)

The primary analysis will be undertaken using a logistic regression model with infection as the outcome and antibody response post-V3 as a binary variable as the exposure. We will present odds ratios with 95% confidence intervals for the unadjusted model, as well as for a model adjusted for the baseline and behavioural variables as well as any COVID-19 therapy received in the community, preadmission and in hospital (where data available).

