Assuming serology is predictive of outcome, we will build a model to explore the predictive value of key patient data and the added value of serological results. We will explore the discrimination and calibration of a model only including baseline and behavioural variables compared to this model also including serological response. Discrimination will be determined by Harrell's C statistic and calibration will be determined by the predicted probabilities for infection. It is not possible to externally validate this model in this study; instead 1000 bootstrapped samples will be used in determining the 95% confidence intervals for the C statistic.

As a sensitivity analysis we will also consider serological response as a continuous variable. We will also consider time to first infection as a time to event outcome with death as a competing risk. This will be implemented in Stata using the *stcrreg* command. The same covariates will be included in the adjusted model as for the primary analysis. Unadjusted and adjusted analyses will present hazard ratios with 95% confidence intervals.

To assess the additive value of serological responses to CV status in predicting severe outcome We will undertake an analysis using the same modelling approach as for the primary outcome but with a composite outcome of severe infection (infection, hospitalisation or death).

Secondary Outcomes

To evaluate the serological vaccine responses of CV patients to new vaccines

28-day post vaccine (Visit 3) IgG antibody levels (BAU/ml) will be reported in HC and CV individuals. The proportion of combined and individual CV groups with no, low or normal Visit 3 antibody levels will be reported.

The median (IQR) of Visit 3 antibody levels in each CV group will be reported, alongside the values for HC.

Logistic regression models will be used to assess factors that contribute to serological response as a binary outcome with normal compared to lack of response (no/low). The model will include the baseline variables set out in **Section 5.2** and further variables may be added to the model if evidence emerges that such variable impacts on vaccine responses to vaccines. Univariable logistic regression will be used to explore the unadjusted relationship of each variable with the outcome and multivariable logistic regression will be used to explore the independent relationship of each variable with the outcome. We will report odds ratios and 95% confidence intervals for all models.

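### The monoclonal-antibody rule stops at the first sample and immunoglobulin recipients are not separated, so passively acquired antibody can be reported as vaccine response or durability

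*Protocol*

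**What the plan says.** Protocol section 5.3 excludes people given an anti-SARS-CoV-2 monoclonal antibody "within the 26 weeks prior to the first study blood sampling". The next sentence reads "Recipients of regular immunoglobulin therapy are eligible", with an asterisk. The asterisked footnote, printed under section 6.1, says: "This enables assessment of the primary outcome and response to bivalent vaccine". It then says that policy on these treatments will probably change and that an amendment may follow.

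In Table 2 (section 5.1), group 9 covers common variable and secondary immunodeficiency needing "prophylactic antibiotics and/or immunoglob" (the last word is broken in the table).

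Section 9.1 says of the anti-spike assay: "It will also detect antibodies following infection and cannot distinguish between these", meaning vaccine-induced and infection-induced antibody.

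Appendix 3, which section 11.0 names as the statistical analysis plan, defines low as "Antibody values which lie within the lower 10th percentile of range of IgG antibody concentrations in HC following vaccine dose". Under its secondary outcomes, "28-day post vaccine (Visit 3) IgG antibody levels (BAU/ml) will be reported in HC and CV individuals" and "The proportion of combined and individual CV groups with no, low or normal Visit 3 antibody levels will be reported". It describes waning as the decline in concentration from Visit 1 to Visit 2 and from Visit 3 to Visit 4. The Visit 1 to Visit 2 decline is compared between healthy controls and clinically vulnerable (CV) participants and by individual group, and the Visit 3 to Visit 4 decline is handled similarly. It does not mention immunoglobulin, or a monoclonal given during follow-up, in any of these analyses.

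**The concern.** The protocol appears to accept that recently infused antibody spoils a vaccine-response measurement, and it guards the first sample for that reason. For most participants, though, the first sample is not the one that measures the response. A monoclonal given between Visit 1 and Visit 3, or between Visit 3 and Visit 4, leaves the participant in the analysis with a result that may reflect the drug.

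Regular immunoglobulin raises the same question in a more lasting form. If the product contains anti-spike antibody, a recipient can be graded normal without having responded, and repeated infusions can make the level look durable.

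Secondary objective (a) is the magnitude and durability of the serological vaccine response, so the group-level and combined results under that objective are at stake.

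**Working it through.** **1. Which samples the monoclonal rule protects.** Visit 3 is 4-10 weeks after vaccination and Visit 4 is 24-36 weeks after (section 6.1, Figure 1 text).
- A dose given between vaccination and Visit 3 is at most 10 weeks old at Visit 3, well inside the protocol's own 26 weeks.
- The gap from Visit 3 to Visit 4 runs from 24 - 10 = 14 weeks to 36 - 4 = 32 weeks. Where it is 26 weeks or less, every dose given after Visit 3 falls inside the 26-week window at Visit 4.
- The rule in section 5.3 reaches none of these doses, because it looks back only from the first sample.
- One exception: under Appendix 6, people recruited after the autumn booster give their first sample at least 28 days, ideally 4-10 weeks, after it. For them the rule does cover the early post-vaccine sample, but not Visit 4.

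**2. Where immunoglobulin recipients sit.** Twenty groups of 120-140 give 20 x 120 = 2400 to 20 x 140 = 2800. Group 9 is 120/2400 = 140/2800 = 5% of that. This is a ceiling for treated people within group 9, since entry is also possible on prophylactic antibiotics alone. The allocation order in section 5.1 puts treatment groups first, then the first applicable disease group, so recipients may also sit in other groups. Their number is not given.

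**3. What Appendix 3 does with their results.**

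| Analysis | Based on | Provision for passive antibody |
|---|---|---|
| No/low/normal at Visit 3 | Measured level against healthy controls | None |
| Median titre by group | Measured level | None |
| Factors associated with response | No/low v normal | Immunoglobulin not among the listed baseline variables; others may be added as evidence emerges |
| Waning | Change in measured level | None |
| Adjusted infection model | Visit 3 class | Adjusts for COVID-19 therapy where data exist |

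The last row is the only therapy adjustment, and it does not reach the first four.

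**4. The plan's own power figure, and a bound for the primary analysis.** Appendix 3 gives 0.15 as the lowest standardised effect for infection. With 750 v 2250, 90% power and two-sided 5%, a 50% rate is detectable against 56.8%. The odds ratio is (0.568/0.432)/(0.5/0.5) = 1.32, and ln(1.32) x sqrt(3)/pi = 0.151. The figure reproduces, and this point does not depend on it.

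As a pessimistic illustration, suppose m of the 750 true low/no responders are graded normal and keep the low-group infection risk. The risk in the normal class becomes (2250 x 0.500 + m x 0.568)/(2250 + m).

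| m | Difference in risk | Power |
|---|---|---|
| 0 | 0.0681 | 90% |
| 35 | 0.0671 | 88% |
| 70 | 0.0661 | 86% |
| 140 | 0.0641 | 81% |

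The last row moves as many people as the whole of group 9 at its upper quota, and it assumes that infused antibody gives no protection.

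**5. Whether the data for a repair exist.** Section 6.5.1 collects regular and previous medication at baseline and asks about drug-history changes at Visits 2-4. The follow-up prompt there concerns immunosuppressive, chemotherapy and radiotherapy changes, so dates of monoclonal or immunoglobulin treatment may need a record check. Sections 6.2 and 6.5.1 provide access to hospital, GP and NHS records.

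**The case against.** The strongest reply is that the immunoglobulin half rests on a fact the documents do not contain. Nowhere do they say that immunoglobulin carries anti-spike antibody, let alone enough to clear the healthy-control 10th percentile. Section 9.1 concerns vaccine versus infection, not infused antibody. This stands: the immunoglobulin half is conditional. The monoclonal half needs no such fact, because the protocol itself excludes these drugs before the first sample. It too has no size, since no rate of use in follow-up is given. The footnote is also awkward evidence: its asterisk is on the immunoglobulin sentence while its text concerns monoclonals, so its purpose is inferred.

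Three stronger readings are tempting and not supported.
- *The primary odds ratio is pulled towards the null.* The primary objective is the predictive value of a measured level, and a level from any source may be a legitimate predictor. Bias towards the null would require that infused antibody protects poorly, which the documents do not address. Even the pessimistic illustration above costs at most about 9 points of power.
- *Secondary objective (a) cannot be answered for treated people.* A steady infused background would not by itself create a rise from before to after vaccination, and results are reported by group, so group 9 is already visible. This softens the point without removing it. Appendix 3 grades the Visit 3 level rather than the rise, Visit 2 can be omitted, and combined summaries and recipients outside group 9 remain mixed.
- *Waning is understated by a definite percentage.* Any such figure only restates an assumed treated share together with an assumption of zero decline in treated people.

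A fuller analysis plan might add flags. However, section 11.0 gives Appendix 3 that role, and the look-back from the first sample is fixed in the protocol itself.

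**Conclusion.** The point holds for the secondary vaccine-response and waning analyses. As written, the Visit 3 and Visit 4 results lack the safeguard that the protocol applies to the first sample, and immunoglobulin recipients are pooled with everyone else. Passively acquired antibody can therefore be reported as response or durability, by group and in combined results.

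The size is not known. The treated share of group 9, recipients in other groups, the anti-spike content of immunoglobulin and the rate of monoclonal use in follow-up are all unstated. No effect on the primary analysis is shown. This is a worthwhile, inexpensive correction to the analysis text, and not a flaw that invalidates the design.

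**What to change.** Amend Appendix 3 only, leaving eligibility and care as they are:

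- (a) Derive a flag for each sample: current regular immunoglobulin, and anti-SARS-CoV-2 monoclonal in the preceding 26 weeks. Use the medication history, the Visit 2-4 change questionnaires and record checks.
- (b) Omit monoclonal-flagged samples from the vaccine-response, factors-of-response and waning analyses, applying the 26-week window to the sample being analysed.
- (c) Report immunoglobulin recipients as a separate stratum in those analyses, and give the combined CV and group summaries with and without them. Excluding them altogether is unnecessary and would thin a group whose response the protocol means to report. The 26-week look-back belongs to the monoclonal rule and has no documented basis for immunoglobulin, so current use is enough for that flag.
- (d) Repeat the primary model without flagged participants, as a sensitivity analysis only.

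The cost is some wording, one derived variable and some record checks for treatment dates. Slightly fewer participants enter some response and waning summaries, mostly in group 9.
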